12.3 Vital Signs (Including Height and Weight)

The averaged values of the 3 measurements collected for blood pressure and pulse at each visit will be used for all summaries and determination of PCIs.

Descriptive statistics for vital signs (sitting systolic and diastolic blood pressure, pulse, height, weight, and BMI) and their changes from baseline at each post-baseline visit and FoTA will be presented by treatment group. In the case of multiple assessments at post-baseline visits, the first readable value at the visit will be used in the summary tables.

Additionally, figures with the mean change from baseline $\pm SD$ of the vital signs values (sitting systolic and diastolic blood pressure, and pulse) will be presented by treatment group and visit.

Height, weight, and BMI will also be converted to percentile values based on the subject's age and sex at each visit and summarized categorically (<5th, 5th to <95th, and ≥95 th) at each visit and at the FoTA. Post-baseline shifts in height, weight, and BMI percentile category (<5th, 5th to <95th, and ≥95 th) from baseline will be summarized at each visit and at the FoTA. In addition, z-scores for height, weight, and BMI will be based on the subject's age at each visit and will be summarized categorically (<-2, ≥-2 to <-1, ≥-1 to <1, ≥1 to <2, and ≥2) at each visit and at the FoTA. Percentiles and z-scores will be derived using the CDC growth charts (Kuczmarski et al, 2002).

Vital sign values will be considered PCI if they meet the criteria listed in Table 4. The number and percentage of subjects with PCI post-baseline values will be summarized by visit and treatment group. The percentages will be calculated relative to the number of subjects with baseline and at least 1 post-baseline assessment. The numerator is the total number of subjects with at least 1 PCI post-baseline vital sign value. A supportive listing of subjects with post-baseline PCI values will be provided including the subject number, site, baseline, and post-baseline PCI values. A listing of all AEs for subjects with post-baseline PCI vital sign values will also be provided. In addition, for pulse, the number and percentage of subjects with at least 1 post-baseline value that fall within the categories >50-<100, 100-<110 and ≥110 beats/minute, will also be summarized by treatment group.

Measurements of oral or tympanic temperature, sitting respiratory rate will be performed at the Screening Visit (Visit 1) only.

^{**} Values taken from the Reviewer Guidance, Conducting a Clinical Safety Review of a New Product Application and Preparing a Report on the Review, Table 7.1.7.3.2.1 pp 70-72. US DHHS FDA CDER, February 2005.

[~]These values were taken from Clinical Laboratory Diagnostics, ed. L. Thomas, MD, Frankfurt, Germany, 1998.

Table 4 Criteria for Potentially Clinically Important Laboratory Tests

Vital Sign Parameter	PCI Criteria
Weight Loss (kg)	≥7% of weight (determined at baseline)
Systolic BP (mmHg), seated	>120*
	>120* on 2 or more consecutive visits
	>10 increase from baseline
	>10 increase from baseline on 2 or more consecutive visits
	>120* and increase >10 from baseline
	>120* and increase >10 from baseline on 2 or more
	consecutive visits
Diastolic BP (mmHg), seated	>80*
	>80* on 2 or more consecutive visits
	>10 increase from baseline
	>10 increase from baseline on 2 or more consecutive visits
	>80* and increase >10 from baseline
	>80* and increase >10 from baseline on 2 or more
	consecutive visits
Pulse (beats/minute)	<=50*
	<=50* and decrease >15 from baseline
	>=100*
	>=100* on 2 or more consecutive visits
	>=100* and increase >15 from baseline
	>=100* and increase >15 from baseline on 2 or more
	consecutive visits
Temperature (tympanic)	>38.0°C (100.4°F)
Temperature (oral)	>37.5°C (99.5°F)
Respiratory Rate (breaths per minute)	<10 or >24

[~]Given the pharmacological effect of the drugs used in ADHD and based on experience gained in previous ADHD trials, the focus is on rise of blood pressure only.

Pulse rate (beats per minute) will be considered abnormal if a value is lower than the 1st percentile or higher than the 99th percentile cut-off values listed in Table 5.

^{*}The NCI has not specified a value, Shire physicians have agreed on values provided.

Table 5 Normal Range of Pulse Rate (beats/min)

Age	1 st Percentile	99 th Percentile
	M	ales
6-8 years	59	114
9-11 years	56	110
12 years	52	108
	Fen	nales
6-8 years	61	117
9-11 years	58	113
12 years	54	110

Source: National health statistics report: Resting Pulse Rate Reference Data for Children, Adolescents, and Adults: United States 1999–2008

https://www.cdc.gov/nchs/data/nhsr/nhsr041.pdf

The number and percentage of subjects with abnormal pulse rate values for at least 1 post-baseline assessment will be tabulated by treatment group for the lower than the 1st percentile and higher than the 99th percentile cut-off values, respectively, for males and females separately. The denominator will be the number of subjects in the Safety Set (per gender) with at least 1 post-baseline pulse measurement. The numerator is the total number of subjects with at least 1 abnormal pulse record. A supportive listing of subjects with abnormal pulse rate values will be provided.

In addition, following the US Department of Health and Human Services standards, blood pressure values higher than the 95th percentile determined by sex, age, and height percentiles will be considered abnormal. The cut-off values are presented in Table 6.

Table 6 95th Percentile Cut-off Values of Blood Pressure Norms by Sex, Age, and Height Percentiles

	Systolic Blood Pressure (mmHg)							Dias	tolic Blood Pressure (mmHg)						
Age (y)		Percentile of Height									Perce	entile of	Height		
							E	Воу	'S						
	5%	10%	25%	50%	75%	90%	95%		5%	10%	25%	50%	75%	90%	95%
6	109	110	112	114	115	117	117		72	72	73	74	75	76	76
7	110	111	113	115	117	118	119		74	74	75	76	77	78	78
8	111	112	114	116	118	119	120		75	76	77	78	79	79	80
9	113	114	116	118	119	121	121		76	77	78	79	80	81	81
10	115	116	117	119	121	122	123		77	78	79	80	81	81	82
11	117	118	119	121	123	124	125		78	78	79	80	81	82	82
12	119	120	122	123	125	127	127		78	79	80	81	82	82	83
							(ir	ls						
6	108	109	110	111	113	114	115		72	72	73	74	74	75	76
7	110	111	112	113	115	116	116		73	74	74	75	76	76	77
8	112	112	114	115	116	118	118		75	75	75	76	77	78	78
9	114	114	115	117	118	119	120		76	76	76	77	78	79	79
10	116	116	117	119	120	121	122		77	77	77	78	79	80	80
11	118	118	119	121	122	123	124		78	78	78	79	80	81	81
12	119	120	121	123	124	125	126		79	79	79	80	81	82	82

Source: National Heart Lung and Blood Institute; May 2004 http://www.nhlbi.nih.gov/guidelines/hypertension/child_tbl.htm

The number and percentage of subjects with any post-baseline blood pressure values higher than the 95th percentile (exclusive) will be tabulated by treatment group and by age group. The denominator will be the number of subjects in the Safety Set (per gender) with at least 1 post-baseline blood pressure measurement. The numerator will be the total number of subjects with at

least 1 blood pressure value higher than the 95th percentile. A supportive listing of all subjects with abnormal blood pressure values will be provided.

All vital signs data will be listed for the Safety Set.

12.4 Electrocardiogram (ECG)

Electrocardiogram results and change from baseline will be summarized at each visit and at the FoTA by treatment group. If there are multiple assessments for the interpretation at any visit, the worst interpretation will be used in the summary tables. For the interval parameters at post-baseline visits, the first readable result will be used if there are multiple assessments.

For the ECG interval parameters, baseline is defined as the average of all valid ECG measurements as the last assessment obtained prior to the first dose of the investigational product. For the ECG interpretation, baseline will be the ECG with the worst interpretation obtained at the baseline Visit (Visit 2), providing this is prior to the first dose of the investigational product.

PCI criteria will be applied to all ECG data at each visit including any repeat/unscheduled assessments and presented by visit and treatment group. PCI criteria are defined in Table 7.

Table 7 Cr	riteria for Potent	ially Clinically	/ Important ECG Valu	ues
------------	--------------------	------------------	----------------------	-----

ECG Parameter	Outlier Criteria
ECG result	Shift from a normal baseline to an abnormal finding or from
	an abnormal baseline to a new abnormal finding
Heart rate	≤50 beats/minute* or ≥100 beats/minute*
PR interval (increase)	≥200 msec*
QRS interval	≥120 msec*
QTcF/QTcB	≥450 msec* and <480 msec*
	≥480 msec* and <500 msec*
	≥ 500msec*
QT/QTc from Baseline	≥30 msec* and <60 msec*
	≥60 msec*

^{*}The NCI has not specified a value, Shire physicians have agreed on values provided. ECG=electrocardiogram; QTcB=Bazett's corrected QT interval; QTcF=Fridericia's corrected QT interval

is the total number of subjects with at least 1 PCI post-baseline ECG value.

The number and percentage of subjects with post-baseline PCI values will be tabulated. The percentages for the observed value criteria will be calculated relative to the number of subjects with at least 1 post-baseline assessment available per parameter and visit. The percentages for the change from baseline criteria will be calculated relative to the number of subjects with available baseline and at least 1 post-baseline assessment per parameter and visit. The numerator

Additionally, a summary table showing the number and percentage of subjects with the Central Reader's assessment of the ECG result as normal, abnormal or unable to evaluate, and the investigator's assessment of abnormal ECG results as not clinically significant or clinically significant at each visit and at the FoTA by treatment group will be produced. A shift table

Version 2.0/16 Aug 2018

showing the change in evaluation from baseline to the FoTA by treatment group will also be produced.

Listings of ECG data including the central reader's assessment and investigator's interpretation by individual subject will be produced. Separate listings will be produced for subjects with ECG results meeting the PCI criteria. Data from unscheduled visits will be listed, but not summarized.

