3.2 Duration and Study Completion Definition

The subject's duration of participation is expected to be approximately 6-10 weeks. The study will be completed in approximately 7 months.

- Planned duration of screening/washout period: up to 32 days
- Planned duration of treatment period: 4 weeks
- Planned duration of safety follow-up: 1 week

The study completion date is defined as the date the final subject, across all sites, completes their final protocol-defined assessment. Please note that this includes the follow-up visit or contact, whichever is later. The study completion date is used to ascertain timing for study results posting and reporting.

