7.1.1.3 Baseline Visit (Visit 2)

Once the screening central clinical laboratory tests and 12-lead ECG results have been obtained, in addition to repeat assessments (if required), and the subject has completed the required washout period (if applicable), the subject will return to the site for the baseline visit (Visit 2).

Inclusion/exclusion criteria must also be reviewed during this visit to ensure subjects continue to meet all eligibility criteria.

Table 1 outlines all procedures to be conducted during the baseline visit (Visit 2) with further clarification provided below:

- For subjects with >32 days since the safety measurements at the screening visit (Visit 1) were collected, an abbreviated physical examination, 12-lead ECG in triplicate, serum pregnancy test, urine drug screen, and all clinical laboratory tests must be repeated, and the results reviewed by the investigator prior to the subject being enrolled.
- Blood pressure and pulse will be collected 3 times (with approximately 2 minutes in between each collection) using the age-appropriate cuff during the visit.
- If >32 days since the screening visit, 3 ECGs will be taken, with approximately 3 minutes in between each one, to ensure appropriate baseline intervals are established. The investigator will perform the initial interpretation of the ECG immediately after collection to ensure the safety of each subject and to determine eligibility. The ECG tracing will be sent to the central reader for analysis. Upon review of the report from the central reader, the investigator will re-evaluate the clinical significance of the ECG in light of other safety data for the subject. If abnormal and significant results are observed following assessment by the central reader, the investigator, in consultation with the appointed CRO Medical Monitor, will confirm the subject's continued participation in this study.

Page 44

- The C-SSRS "since last visit" version should be completed.
- For eligible subjects, the investigator or assigned site staff designee will access the IWRS to enroll the subject and obtain an investigational product bottle number to dispense to the subject. Subjects will be dispensed a 9-count bottle of investigational product to cover them until their next regularly scheduled visit. Subjects will be instructed to take 1 capsule each day. Dosing will begin the morning following the baseline visit (Visit 2).

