7.2.4.8 Electrocardiogram

A 12-lead ECG will be performed at the screening visit (Visit 1), Visit 4, and Visit 6/ET. At screening, 3 ECGs taken approximately 3 minutes apart will be collected; if >32 days have passed since screening, these ECGS will be collected in triplicate at Visit (Visit 2) to ensure appropriate baseline intervals are established. Additional ECGs may be performed during the study at the investigator's discretion.

Page 52

07 September 2017

All ECGs will be performed after 3 minutes of rest using the central ECG provider's equipment and will be sent to the central ECG provider electronically.

The initial interpretation of the ECG, normal or abnormal and clinical significance, will be performed immediately after collection to ensure the safety of each subject. An ECG tracing will then be evaluated by a cardiologist at a central ECG reading vendor and returned to the site with a determination of normal or abnormal. Upon review of the report from this vendor, the investigator will re-evaluate the clinical significance of the ECG while taking into consideration all other safety data available for the subject.

Although a central ECG reader is being used for this study, the eligibility of the subject is based on the investigator's assessment of the ECG. If abnormal and significant results are observed following assessment by the central reader, the investigator, in consultation with the appointed CRO medical monitor, reconfirms subject eligibility to continue.

All ECGs transmitted to the central ECG reader will be analyzed. If the central ECG reader receives multiple ECGs, the first readable ECGs will be analyzed as the scheduled ECG. Every ECG transmitted to the central ECG reader will have corresponding source document data collected. No ECG should be deleted by study site personnel. All ECGs must be transmitted to the central provider regardless of quality, results, or number of ECGs taken at a respective visit.

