2. STUDY DESIGN

2.1 General Study Design

This study is a Phase 3 randomized, double-blind, multi-center, parallel-group, placebo-controlled, fixed-dose, efficacy, and safety study in which children aged 6-12 with attention-deficit/hyperactivity disorder (ADHD) will be randomized at baseline (Visit 2) in a 1:1 ratio to SHP465 6.25 mg or placebo for 4 weeks of double-blind treatment as outlined in Table 1.

[figure not shown]
The study will have up to 3 periods as outlined below and in Figure 1:

- Screening and washout period (up to 32 days)
- Treatment period (4 weeks)
- Safety follow-up period (1 week)

Approximately 60 subjects will be randomized in this study to evaluate the efficacy and safety of SHP465 6.25 mg, administered as a daily morning dose in the treatment of children aged 6-12 years with ADHD. Approximately 50% of the total number of subjects will be aged 6-8 years and approximately 50% of subjects will be aged 9-12 years. Approximately 25% of all subjects will be female.

This study will be conducted at approximately 45 sites in the United States (US).

Figure 1 Study Design Flow Chart

ET=early termination; V=visit; W=week

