- Whenever possible, the same individual should complete/rate consistently the following scales and questionnaires as appropriate: ADHD-RS-5, CGI-S/I, and subject check to remain in the study; and the same caregiver/LAR for PSQ and CSHQ. Include assessment of decreased appetite.
- If > 32 days have elapsed since the screening evaluation was completed at Visit 1, then the following evaluations must be repeated at baseline (Visit 2): vital signs, serum pregnancy test, urine drug screen, clinical laboratory evaluations, and ECGs in triplicate. The physical exam will be abbreviated with a review of the following body systems: general appearance, respiratory, and cardiovascular.
- h Height and weight will be measured without shoes and with light clothing using a calibrated stadiometer for height and calibrated scale for weight.
- Vital signs include oral or tympanic temperature, pulse, sitting blood pressure, and respiration rate. The subject will have been seated for a minimum of 3 minutes before blood pressure, pulse and respiration rate measurements are taken. Measurement of blood pressure and pulse will be collected 3 times (with approximately 2 minutes in between each collection). The average of each set of 3 measurements will be used to determine continued participation in the study.
- Blood pressure and pulse rate will be measured at each study visit. Temperature and respiration rate will be measured at screening (Visit 1) and/or baseline (Visit 2) only.
- ^k For females of child-bearing potential only.
- Electrocardiograms will be recorded in triplicate with approximately 3 minutes in between each collection at screening only and at baseline only if >32 days have elapsed since the screening evaluation was completed at Visit 1.

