12. SAFETY ANALYSES

Safety data will be analyzed for the Safety Set. Safety endpoints include the occurrence of TEAEs, vital signs (systolic and diastolic blood pressure, pulse, temperature, and respiration rate), height and weight, ECG results, C-SSRS, PSQ, and CSHQ. For each safety endpoint, the last value collected before the first dose of double-blind investigational product will be used as baseline for all analyses of that safety endpoint. Except for AE data, only post-baseline assessments from Visit 2 (Week 0) up to Visit 6 (Week 4) that were collected on or before 2 days after the last dose of double-blind investigational product will be analyzed. A Final on-Treatment Assessment (FoTA) will be defined as the last valid assessment obtained after Baseline and whilst on investigational product (on or before 2 days after the last dose date).

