19.4 Repeated or Unscheduled Assessments of Safety Parameters

If a subject has repeated assessments before the start of double-blind investigational product, then the results from the final assessment made prior to the start of double-blind investigational product will be used as baseline.

Protocol SHP465-309

If a subject has repeated assessments at any post-baseline visit, the first recorded assessment will be assigned to the visit for generating descriptive statistics. For vital signs (sitting systolic and diastolic blood pressure, and pulse), this will be the average of the 3 measurements from the first recorded assessment.

If final on-treatment safety assessments are repeated or unscheduled, the last post-baseline assessment will be used as the final on-treatment assessment for generating descriptive statistics. For vital signs (sitting systolic and diastolic blood pressure, and pulse), this will be the average of the 3 measurements from the last post-baseline assessment.

However, all post-baseline assessments will be used for PCI value determination and all assessments will be presented in the data listings.

All repeat and unscheduled visits will be listed.

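### SAP 12.4 takes the baseline ECG interpretation from Visit 2, where an on-schedule child has no planned ECG, so the two interpretation shift outputs lose their baseline if the rule is followed literally

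*SAP*

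**What the plan says.** SAP Section 12.4 gives two baseline rules in one paragraph. For the interval parameters, baseline is the average of the valid measurements at the last assessment before first dose, whichever visit that was. For the normal/abnormal reading the rule is tied to a visit: "For the ECG interpretation, baseline will be the ECG with the worst interpretation obtained at the baseline Visit (Visit 2"), on condition that it precedes the first dose.

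The ECG schedule is as follows:

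- Protocol 7.2.4.8, routine ECGs: "A 12-lead ECG will be performed at the screening visit (Visit 1), Visit 4, and Visit 6/ET".
- Protocol 7.1.1.3, at Visit 2: "If >32 days since the screening visit, 3 ECGs will be taken, with approximately 3 minutes in between each one".
- SAP 2.4, footnote to the schedule, triplicate ECGs: "at screening only and at baseline only if >32 days have elapsed since the screening evaluation was completed at Visit 1".
- Protocol 3.2: "Planned duration of screening/washout period: up to 32 days". SAP 2.1 gives the same limit: "Screening and washout period (up to 32 days").

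SAP Section 12 sets a general rule for every safety endpoint: "the last value collected before the first dose of double-blind investigational product will be used as baseline". For assessments repeated before dosing, SAP 19.4 says that "the results from the final assessment made prior to the start of double-blind investigational product will be used as baseline".

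**The concern.** The SAP takes the interpretation baseline from a visit at which an on-schedule subject has no planned ECG. The condition that the ECG must precede the first dose does not help. Dosing starts the morning after Visit 2 (Protocol 6.2.3), so a Visit 2 ECG is pre-dose anyway, and the condition says nothing about a Visit 2 ECG that was never taken.

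Two outputs in SAP 12.4 need this baseline: the ECG result criterion in Table 7, which counts shifts from a normal baseline to an abnormal finding or from an abnormal baseline to a new abnormality, and the table of shifts in evaluation from baseline to the final on-treatment assessment. SAP 12.6 also calls for ECG summaries within each age group.

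For change-from-baseline criteria, 12.4 counts in the denominator only subjects with an available baseline. Applied literally, on-schedule subjects leave the shift percentage, and those who remain are the ones with an unusually long screening period. For a stimulant, with ECG results named in the secondary safety objective, these tables should rest on all treated children with usable ECGs.

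**Working it through.** The plan states no figure to reproduce. The check sets the baseline rules against the ECG schedule and then sizes the result.

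**Step 1. Which pre-dose ECG exists for whom**

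| Days from screening to Visit 2 | Scheduled pre-dose ECG | Interpretation baseline, 12.4 literal | Baseline under the Section 12 rule |
|---|---|---|---|
| 32 or fewer (as planned) | Visit 1 triplicate | none | Visit 1 |
| More than 32 | Visit 1 and Visit 2 triplicates | Visit 2 | Visit 2 |

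The two rules agree only for subjects outside the planned window. A discretionary ECG at Visit 2 is allowed (Protocol 7.2.4.8) but not planned.

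**Step 2. How many subjects**

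Inputs: about 60 randomized, 30 per arm (Protocol 9.7). The documents do not give the share beyond 32 days; 5% to 30% is assumed for illustration.

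- All within the window: 60 × 0 = 0 with a baseline, 60 without (100%).
- 5% beyond: 60 × 0.05 = 3 with, 57 without (95%).
- 30% beyond: 60 × 0.30 = 18 with, 42 without (70%).

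**Step 3. What that does to a percentage**

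At the 30% end, with an even split, 18 / 2 = 9 subjects per arm have a baseline instead of 60 / 2 = 30. One shift then reads as 1/9 = 11.1% instead of 1/30 = 3.3%.

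**Step 4. Where overruns are plausible**

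Washout should start only after the screening laboratory and ECG results have been reviewed (Protocol 7.1.1.2). The washout lengths in Protocol Table 2 leave this much of the 32 days:

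- 30-day washout: 32 − 30 = 2 days
- 14-day washout: 32 − 14 = 18 days
- 7-day washout, which includes psychostimulants: 32 − 7 = 25 days

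Overruns are thus likely mainly for the 30-day classes. The lower the true overrun share, the closer the literal rule comes to leaving nobody with a baseline.

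**The case against.** The strongest reply is that a baseline is not really absent. SAP Section 12 covers every safety endpoint, names ECG results among them, and uses the last pre-dose value. A programmer who finds no Visit 2 record can follow that rule, or the neighbouring interval rule, to the screening ECG. On this view the defect is an unstated order of precedence between two rules. That is fair, and it is why nothing is irretrievably lost. It does not remove the conflict: 12.4 is the more specific text and deliberately treats interpretation differently from intervals, so a programmer could equally take it as governing.

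Other points on that side:

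- Section 19.4 is weak support. It applies only where assessments were repeated before dosing, and the subject at issue is the one with no repeat. The contradiction rests on Section 12 and on the interval rule in 12.4.
- The 11.1% against 3.3% contrast uses the upper end of an assumed range. With very few overruns the shift table would be nearly empty, and someone would probably notice. This stands; the contrast is an illustration, not a forecast.
- SAP 12.4 does not say expressly that the ECG result shift is a change-from-baseline criterion. That reading is natural. If the other denominator were used, subjects without a baseline would stay in it but could never count as a shift, so the percentage would be understated.
- The outputs are descriptive, the ECG data are listed by subject, and the table specifications are in a separate document that may already settle the rule. All true; this limits the consequence but leaves the SAP at odds with its own schedule.

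**Conclusion.** The concern holds. As written, 12.4 leaves subjects who keep to the planned screening window without a baseline ECG interpretation, contrary to the SAP's own last-pre-dose rule. Under the literal reading this affects all of about 60 subjects if the window is kept, or 42 to 57 of 60 if an assumed 5% to 30% overrun it. These counts presume that no discretionary ECG was taken at Visit 2 and that no programming rule elsewhere overrides the sentence.

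The damage is confined to the two interpretation shift outputs and any age-group versions of them. Interval and QTc analyses, counts of interpretations by visit and at the final on-treatment assessment, listings, efficacy analyses and subject management are untouched. It should be fixed, but it does not threaten the trial's main conclusions. Confidence is high on the wording conflict; whether subjects would actually drop out of the tables depends on how the rule is programmed.

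**What to change.** Before unblinding, replace the interpretation sentence in SAP 12.4 with, for example: *For the ECG interpretation, baseline is the worst interpretation among the ECGs in the last ECG assessment set obtained before the first dose of investigational product (Visit 1, or Visit 2 if repeated).* This keeps the worst-reading principle and agrees with Section 12 and the interval rule, which needs no change. It would help to add whether an unscheduled pre-dose ECG can serve as that last set, since 12.4 lists unscheduled data without summarizing them. The table specifications should be checked for the same rule.

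The cost is one SAP sentence and the matching derivation. The screening triplicate is already collected for every subject, so no new data or change in procedures is needed.
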